10.1 Schedule of Events

Protocol required follow-up evaluations should be performed at the trial site. Remote visits via phone contact are permitted, if necessary. The protocol required evaluations for each trial interval are listed as follows and summarized in Table 2.

10.1.1 Screening and Enrollment Procedures

Refer to the Optimize PRO parent protocol for screening and enrollment procedures. Training specific to implanting the Evolut FX TAV will be required prior to enrolling in the addendum.

10.1.2 Implant Procedure (TAVR) and peri-procedural data collection

Refer to the Optimize PRO parent protocol for details pertaining to the implant procedure, pre- and periprocedural data collection, including 12-lead ECG timepoints, required laboratory tests, and procedural angiograms confirming cusp overlap view. In addition to the views specified in the Optimize PRO parent protocol, fluoroscopy images in the **LAO view** are required to be saved at the following two time points:

- Prior to crossing the aortic arch
- In the ascending aorta prior to switching to RAO view, ideally immediately prior to crossing the annulus

If the aortic arch is recrossed for the purpose of aligning the commissures, a second set of the two images listed above will be required.

A post-procedure MSCT with contrast has been added for the purpose of assessing coronary-commissure overlap, and can be collected anytime post-procedure through the 30 day follow-up visit.

Procedural aspects specific to the Medtronic TAVR system should be performed according to the Instructions for Use.

The valve deployment will be completed in accordance to the cusp overlap technique via procedural angiogram, and the standard procedures of the implanting physicians and the TAVR clinical pathway protocol requirements noted in the Optimize PRO parent protocol. This described TAVR clinical pathway should serve as a guide for accelerated discharge. Institutional clinical TAVR pathways can be followed as long as the modifications are consistent with an accelerated discharge.

Version 3.0

Page 19 of 29

10.1.2.1 External ECG Monitors

The conduction disturbance pathway indicates in some circumstances that the subject should be discharged home with an external ECG monitor (Holter monitor). Holter monitors will be provided to participating sites for the FX addendum.

10.1.3 Follow-Up Evaluations

Refer to the Optimize PRO parent protocol for requirements for 30-day and 12-month follow-up visits. Note a Modified Rankin Score assessment should be conducted at 1 and 3 months following any stroke event.

10.1.3.1 Visit Windows

Day 0 = day of index procedure

- 30 Day (30 + 14 days)
- 12 months (365 ± 30 days)

Version 3.0

Page 20 of 29

[figure not shown]

Table 2. Summary of Visit Schedule and Required Evaluations

	Screening	TAVR Procedure	Discharge	30 Days	12 Months
Informed Consent and HIPAA Authorization	х				
Clinical Assessment (Physical Assessment and Concomitant Medications)	x		x	х	х
NYHA Classification	Х		Х	Х	Х
TTE	Х		X ⁶		X
MSCT Angiogram	Х		X ⁷		
Procedural Angiogram		X			
Laboratory Test	Х		X		
12-Lead ECG ¹		X ⁵	X	X	Х
Modified Rankin Score ²	Х				
Quality of Life Questionnaires ³	Х			Х	Х
STS Risks Assessment	Х				
Katz Index of Independence in Activities of Daily Living	х				
5-Meter Gait Speed	Х				
Grip Strength	Х				
Pacemaker Interrogation⁴				X	Х
Adverse Event Review		X	X	X	X

¹Refer to Appendix 18.1 of the Optimize PRO parent protocol - Conduction Disturbance Management for discharge 12-lead ECG requirements.

10.1.4 **Additional Evaluations for Pacemaker Implants**

Refer to the Optimize PRO parent protocol for requirements for interrogation of implanted permanent pacemakers.

² A Modified Rankin Score assessment should be conducted at 1 and 3 months following any stroke event.

³ Quality of Life Questionnaires include EQ-5D and KCCQ.

⁴ In-office pacemaker interrogations at pacemaker implant, 30-days, and 12 months and CareLink™ Transmissions at 3, 6, and 9 months required for subjects implanted with pacemakers post index TAVR procedure.

⁵ ECGs are required within 48 hours pre-procedure and then again within 2 hours post-procedure. Depending on the Conduction Disturbance pathway the subject is in post-procedure, additional ECGs may be required at 24 hours and 48 hours post-procedure.

⁶ Discharge TTE should be done between 12 hours and 7 days post TAVR

⁷ Post-procedure CT may be conducted anytime post-procedure through the 30 day follow-up visit. This CT must be conducted with contrast to allow for proper assessment of anulus location relative to implanted TAV.

Version 3.0

Page 21 of 29

10.1.5 Missed Follow-Up Visits

Refer to the Optimize PRO parent protocol for instructions on the handling of missed follow-up visits.

10.1.6 Core Labs

Refer to the Optimize PRO parent protocol for details on Core Labs utilized for this study. The ECG Core Lab will not be utilized for the FX Addendum.

10.1.7 Subject Consent

A separate subject consent form will be provided for this addendum. Refer to the Optimize PRO parent protocol for instructions pertaining to obtaining subject consent and revisions to informed consent forms.

10.2 Assessment of Efficacy

Refer to the Optimize PRO parent protocol for assessments of efficacy.

10.3 Assessment of Safety

Refer to the Optimize PRO parent protocol for assessments of safety including adverse events and device deficiencies.

10.4 Device Malfunction or Explant

Refer to the Optimize PRO parent protocol for instructions pertaining to device malfunction or explant.

10.5 Data Collection

Refer to the Optimize PRO parent protocol for details pertaining to data collection.

10.5.1 Source Documents

Refer to the Optimize PRO parent protocol for source documentation requirements.

10.6 Deviation Handling

Refer to the Optimize PRO parent protocol for details on deviation handling.

Version 3.0

Page 22 of 29

10.7 Subject Exit, Withdrawal or Discontinuation

Refer to the Optimize PRO parent protocol for details on subject exit, withdrawal or discontinuation.

11 Risks and Benefits

11.1 Potential Risks

There are possible risks and side effects connected to the Evolut[™] FX TAV implant, but the risks are the same as those for an implant of the Evolut FX[™] TAV without participation in this study, with the exception of the incremental risks associated with the post-procedure CT scan. Standard risks associated with use of the Evolut[™] FX system in the study are provided in the Instructions for Use.

Risks and events will be continuously monitored, assessed, and documented by the investigator.

11.2 Potential Benefits

Participation in this clinical study will not result in any direct benefit to the patient. Trial subjects implanted with an Evolut™ FX device receive the same medical treatment as if they were not participating in this post-market study. Participation contributes to expansion of the knowledge base with respect to the use of the Evolut™ FX system in a routine hospital setting.

11.3 Risk-Benefit Rationale

Refer to the Optimize PRO parent protocol for discussion on risk minimization, alternative therapies, and results from the risk analysis and justification for this study.

12 Adverse Events and Device Deficiencies

[figure not shown]
Refer to the Optimize PRO parent protocol for requirements pertaining to Adverse Events and Device Deficiencies.

12.1 Emergency Contact Details for Reporting AEs and Device Deficiencies

Investigators should contact their Medtronic clinical trial monitor or site manager if they have any questions regarding reportable AEs. Medtronic will provide and maintain a listing of current contact details for each site.

Version 3.0

Page 23 of 29

13 Statistical Design and Methods

13.1 General Aspects of Analysis

13.1.1 Enrolled Population

Within the enrolled population the following analysis sets are distinguished:

- The attempted implant set: The attempted implant set consists of all enrolled subjects with an attempted TAVR implant procedure, defined as when the subject is brought into the procedure room and any of the following have occurred: anesthesia or conscious sedation administered, vascular line placed, TEE placed, or any monitoring line placed. Subjects will be analyzed according to their first attempted procedure. Enrolled subjects that do not receive an attempted TAVR implant are to be exited from the study.
- The implanted set: The implanted set consists of all the attempted implant subjects who are actually implanted with the TAV. Subjects with an attempted implant that do not actually receive a TAV are to be exited from the study following discharge from the index hospitalization.
- Per protocol (PP) set 1 for TAVR care pathway: This per protocol set consists of all implanted subjects with percutaneous and transfemoral access only and no concomitant procedures including percutaneous coronary intervention (PCI). This per protocol set 1 will be used for the secondary endpoint median days from index procedure to discharge. Time zero begins on the date of the first attempted implant procedure.
- Per protocol (PP) set 2 for conduction disturbance pathway: This per protocol set consists of all
 attempted implant subjects whose peri and post TAVR index procedure follows the conduction
 disturbance pathway management and cusp overlap technique. This per protocol set 2 will be used
 for the secondary endpoint rate of pacemaker implant for new onset or worsening conduction
 disturbance at 30 days.

The primary analysis for the primary objective and secondary safety and effectiveness objectives will use the attempted implant set.

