13.3 Primary Analysis

The study objective and endpoints are descriptive, and no statistical hypothesis testing will be performed. The primary endpoint analysis will be conducted after the last subject has had the opportunity to be followed through 30 days post procedure.

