8.1. Study Subjects

8.1.1. Disposition of Subjects

Subjects disposition will be summarized, including the number of subjects enrolled, attempted implant, implanted, died, withdrawn, lost-to follow up, and completed each scheduled follow up visit during the study.

Clinical Investigation Plan (CIP) Deviations 8.1.2.

Protocol deviations will be reported regardless of whether medically justifiable, pre-approved by Medtronic, or taken to protect the subject in an emergency. CIP deviations will be summarized by follow up visit.

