8.1.3. Analysis Sets

Within the enrolled population (subjects who signed consent form) the following analysis sets are distinguished:

- The attempted implant set: The attempted implant set consists of all enrolled subjects with an attempted TAVR implant procedure, defined as when the subject is brought into the procedure room and any of the following have occurred: anesthesia or conscious sedation administered, vascular line placed, TEE placed, or any monitoring line placed. Subjects will be analyzed according to their first attempted procedure. Enrolled subjects that do not receive an attempted TAVR implant are to be exited from the study. Time zero begins on the date of first attempted implant procedure.
- The implanted (IMP) set: The implanted set consists of all the attempted implant subjects who are actually implanted with the Medtronic TAV device. Subjects with an

Version 5.0

Page 13 of 21

attempted implant that do not actually receive a TAV are to be exited from the study following discharge from the index hospitalization. Time zero begins on the date of first attempted implant procedure.

- Per-protocol (PP) set 1 for TAVR care pathway: This per-protocol set 1 consists of all implanted subjects with percutaneous and transfemoral access only and no concomitant procedures including percutaneous coronary intervention (PCI). This per-protocol set 1 will be used for the secondary endpoint median days from index procedure to discharge. Time zero begins on the date of first attempted implant procedure.
- Per-protocol (PP) set 2 for conduction disturbance pathway: This per-protocol set 2 consists of all attempted implant subjects whose peri- and post-TAVR index procedure follows the conduction disturbance pathway management and cusp overlap technique. The cusp overlap technique followed can be defined as the 4 essential COT steps followed, which means the MUO case evaluation step 1, step 2 and/or 3, step 5 and step 15 are each followed. This per-protocol set 2 will be used for the secondary endpoint rate of pacemaker implant for new onset or worsening conduction disturbance at 30 days.
- **Roll-in:** Roll-in subjects will not be analyzed with the study cohort attempted implant, implanted, or per protocol sets and will be analyzed separately using descriptive statistics.

Index Procedure 8.1.4.

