8.2. General Methodology

Descriptive statistics will be used to report study data.

For continuous variables (e.g., age), the mean, median, standard deviation, minimum, maximum, and first and third quartiles will be presented. For categorical variables, the number and percentage of subjects in the category of interest will be presented.

For time to event variables, Kaplan-Meier analyses of event or event-free rates at 1 and 12 months will be presented. For these analyses, the time points will correspond to 30 days and 365 days post-implantation, respectively. At each time point with data, the product limit estimate of the event or event-free rates will be presented. In addition, 95% confidence interval using the Greenwood standard error will be presented. For subjects without an event, the date of censoring will be the latest date of all follow-up visits, assessments, and events (for nondeath events).

Version 5.0

Page 14 of 21

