8.3. Missing Data

Every effort will be undertaken to minimize missing data. However, some missing data is inevitable, and the trial is designed with the expectation that there may be up to 6% of primary data missing at 12 months. Unless otherwise specified, no statistical techniques will be used to impute missing data. The number of subjects included in each analysis will be reported so that the reader can assess the potential impact of missing data.

In the case of partial dates, if only the month and year are known, the event or assessment will be analyzed as if it occurred on the 15th of that month. If only the year is known, the event or assessment will be analyzed as if it occurred on June 30th of that year. These resolutions of partial dates are subject to the restrictions that events must occur no earlier than the procedure date.

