9.5. Statistical Methods

Refer to Section 8 for details on the statistical analysis for the Optimize PRO study. The roll-in analysis set will not be applicable for the FX Addendum. The analysis will be descriptive, and no statistical hypothesis tests will be performed.

Version 5.0

Page 20 of 21

The attempted implant set, implanted set, PP set 1 for TAVR care pathway, and PP set 2 for conduction disturbance pathway will be defined the same for subjects enrolled in the FX Addendum.

The primary analysis cohort for the primary endpoint and secondary safety and effectiveness endpoints will be the attempted implant set. Secondary and additional exploratory endpoints will be analyzed for both the attempted implant set, per protocol (PP) set 1 for TAVR care pathway cohort, and per protocol (PP) set 2 for Conduction Disturbance pathway. However, Percentage of subjects with an NCC depth of implant between 1.0 and 5.0 mm, Percentage of subjects with an absolute canting value |NCC-LCC| of ≤ 2.0 mm, Percentage of subjects in which the target depth of implant was achieved, and Echocardiography data will be analyzed based on the implanted set.

All post-reintervention echocardiographic data will be excluded from hemodynamic analyses unless specified otherwise. Echocardiographic assessments after the first reintervention date will be excluded from any analyses using echo data. Reinterventions will be based on CEC adjudication.

Changes to Planned Analysis 10.

The planned analyses in this SAP are aligned with the planned analyses noted in the CIP (6.0, 04 May 2021). Additionally, all analyses defined for the FX Addendum are consistent with the version of the Addendum for which this plan was developed (3.0, 15 December 2022).

11. **Validation Requirements**

Level 1 validation (independent validation) will be used for the analysis datasets and the primary and secondary endpoints. Level 2 validation (peer review) will be used for additional analyses, data summaries, and listings.

References 12.

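### Subjects with an attempted implant but no valve are exited at index discharge, yet they belong to the set in which 30-day death or stroke is the primary endpoint

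*Protocol*

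**What the plan says.** **Exit rule.** Protocol 13.1.1, in defining the implanted set, states that attempted-implant subjects who "do not actually receive a TAV are to be exited from the study following discharge from the index hospitalization". SAP 8.1.3 has the same rule: subjects with an "attempted implant that do not actually receive a TAV are to be exited from the study" once the index hospital stay ends. SAP 9.5 carries it into the addendum, because the analysis sets "will be defined the same for subjects enrolled in the FX Addendum".

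**Primary cohort and endpoint.** SAP 9.5: "The primary analysis cohort for the primary endpoint and secondary safety and effectiveness endpoints will be the attempted implant set". Protocol 13.1.1 agrees. The primary endpoint is all-cause death or any stroke at 30 days, by Kaplan-Meier (Protocol 13.3.1, SAP 8.8.1), with time zero at the first attempted procedure (SAP 8.1.3).

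**Timing.** Protocol 13.3 runs the primary analysis "after the last subject has had the opportunity to be followed through 30 days post procedure".

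**Censoring and missing data.** For subjects without an event, SAP 8.2 says "the date of censoring will be the latest date of all follow-up visits, assessments, and events". SAP 8.3 adds that, unless otherwise specified, "no statistical techniques will be used to impute missing data".

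**Disposition.** SAP 8.1.1 will summarize subjects, "including the number of subjects enrolled, attempted implant, implanted, died, withdrawn", as well as losses to follow-up and completed visits.

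**Deferred.** The 30-day visit requirements (Protocol 10.1.3), subject exit (10.7) and missing data (13.7) are left to the parent protocol, which was not among the documents reviewed.

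**The concern.** An attempted-implant set exists so that failed and aborted attempts count. Here these subjects stay in the set, but observation of them ends by rule at discharge, usually well before day 30 in a study built around accelerated discharge. This is missing follow-up by design, not ordinary loss.

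Kaplan-Meier gives a censored subject the later risk of those still followed, nearly all of whom have a valve. That is sound only if censoring is unrelated to risk. Here it is triggered by the outcome of the procedure, so it may be informative. If subjects who leave hospital without a valve have a higher risk up to day 30, the primary rate is too low for the population it is said to describe, and the Greenwood interval does not reflect that.

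The 30-day pacemaker rate, the readmission rates and the 1-year composite share the gap. No direction of bias is claimed for pacemaker implantation or readmission.

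**Working it through.** There is no planned figure to reproduce: the 150 subjects in Protocol 13.4 are not statistically derived, and no event rate is given.

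**Step 1: follow one subject through the rules.** A subject is sedated, so the attempt counts under 13.1.1. No valve is implanted, and the subject is discharged event-free.

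- The subject is in the primary set (Protocol 13.1.1, SAP 9.5).
- The subject is exited at discharge (Protocol 13.1.1, SAP 8.1.3).
- The subject is censored at last contact, about the day of discharge (SAP 8.2), with nothing imputed (SAP 8.3).
- A stroke or death after discharge and before day 30 does not enter the estimate. Deaths and strokes in hospital do.

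Table 2 of the protocol lists a 30-day visit but makes no exception to the exit rule. Section 13.3 fixes only when the analysis is run.

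**Step 2: expected understatement.** Assumptions, since the documents give none: k = 2, 3 or 5 subjects exited event-free before day 30; risk p0 = 2% or 3% in the others; risk q from p0 up to 30% in those exited. N = 150 is from Protocol 13.4.

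Understatement ≈ (k/150) × (q − p0)

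- q = p0: zero.
- Smallest non-zero case: (2/150) × (0.05 − 0.03) = 0.03 points.
- Middle case: (3/150) × (0.10 − 0.02) = 0.16 points.
- Largest case: (5/150) × (0.30 − 0.02) = 0.93 points.

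For comparison, the 95% half-width at a 2% rate is 1.96 × √(0.02 × 0.98/150) = 2.24 points. One event is 1/150 = 0.67 points.

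**Step 3: planned estimate against the possible range.** Assume 3 observed events, a of them before the k subjects are censored and 3 − a after.

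Kaplan-Meier rate = 1 − (1 − a/150) × (1 − (3 − a)/(150 − a − k))

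If all 150 had known day-30 status, the rate would lie between 3/150 and (3 + k)/150.

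| k exited | Kaplan-Meier (a = 3 to a = 0) | Best to worst case |
|---|---|---|
| 2 | 2.00–2.03% | 2.0–3.3% |
| 3 | 2.00–2.04% | 2.0–4.0% |
| 5 | 2.00–2.07% | 2.0–5.3% |

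With 5 observed events (3 before censoring, 2 after) and k = 3, the estimate is 1 − (1 − 3/150) × (1 − 2/144) = 3.36%, against a range of 3.33% to 5.33%.

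The estimate stays near the best case whatever happens to the exited subjects. The upper bound requires every one of them to have an event, so it is a limit and not an expectation.

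**The case against.** **The parent protocol may already deal with this.** It governs the addendum and holds the rules on exit, visits and missing data. This stands as a limit: a status check there cannot be excluded. But the addendum states its own exit rule without qualification, and a reader following it would stop at discharge.

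**The effect is small and rests on assumed inputs.** This also stands. Every case in Step 2 is below the sampling half-width; the largest is 0.93/2.24, about 42% of it. Many attempts may stop for benign reasons, since sedation or a line is enough to count as an attempt. A subject implanted at a second attempt before discharge would not be exited, which lowers k. With few events, Kaplan-Meier sits near the best case for any small censored group, so Step 3 does not by itself show bias.

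**The plan already discloses missing data.** SAP 8.3 expects up to 6% of primary data missing at 12 months and reports the number analyzed; 2 to 5 of 150 is 1.3% to 3.3%. SAP 8.1.1 gives attempted and implanted counts and visit completion, and SAP 8.9 lists deaths and dated adverse events. The number exited could largely be pieced together from these. But no planned output states how many were exited event-free before day 30, and the 6% is not specific to day 30 or to these subjects.

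**Section 13.3 promises no one 30 days of follow-up.** Correct: it sets the timing of the analysis. The point rests on the exit rule, not on 13.3.

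**Conclusion.** The concern holds and should be fixed. As written, the plan includes attempted-implant subjects without a valve in the primary 30-day set and stops observing them at discharge, so their later deaths and strokes cannot be counted and their censoring depends on the outcome of the procedure. Under the stated assumptions the primary rate is understated by about 0.03 to 0.93 points, and by zero if their risk equals that of the others. The study is descriptive, so no test or pass/fail decision is affected. It is worth correcting because this is the headline rate, few events are expected, and the repair is cheap. Confidence is medium: the number of such subjects and their risk are unknown, and the parent protocol was not seen.

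**What to change.** Amend Protocol 13.1.1 and the matching text in SAP 8.1.3 and 9.5 so that, for every attempted-implant subject, vital status and stroke are ascertained through day 30 by phone or records before exit. If the parent study's 650-subject cohort is to stay untouched, confine the change to 13.1.1 and SAP 9.5. If the parent protocol already requires the check, cite it in 13.1.1.

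If subjects have already been exited, report k, the number exited event-free before day 30. Beside the Kaplan-Meier estimate give the bounds e/150 to (e + k)/150, where e is the number of subjects with an observed event by day 30 and 150 is replaced by the actual size of the set. The bounds treat all other subjects' day-30 status as known.

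The cost is a short amendment and a call or records check for a handful of subjects. Protocol 10.1 already permits phone contact for required visits; the amendment would need to extend that to these subjects. The fallback is two extra lines of output. The reported rate may become slightly less favourable.
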